^[1] Common effect for the strata (co-medication type*median Baseline Pain NRS) specific risk difference, representing common difference in probability across strata.

^[2] P-value < 0.05 indicates a significant association between number of subjects with >=30% decrease from Baseline and treatment across strata. Reference Listing: 16.2.6.1

[figure not shown]

Table 14.2.6.2 Daily Pain NRS Responder Analysis (≥30%): GEE Analysis (Observed Cases) mITT Population

Model parameter estimates

Parameter	Estimate	Z value	Degrees of freedom	Standard Error	2-sided 95% CL	2-sided P-value [2]
Intercept	XX.XX	XX.XX		XX.XXX		•
Co-medication type			XX			0.xxxx
Week			4			0.xxxx
Treatment			3			0.xxxx
Treatment*Week			12			0.xxxx
Active 5 mcg vs Placebo	XX.XX	XX.XX	1	XX.XXX	[x.xx to x.xx]	0.xxxx
Active 150 mcg vs Placebo	XX.XX	XX.XX	1	XX.XXX	[x.xx to x.xx]	0.xxxx
Active 450 mcg vs Placebo	XX.XX	XX.XX	1	XX.XXX	[x.xx to x.xx]	0.xxxx
Dispersion	XX.XX					

CL = Confidence limits; GEE: Generalized Estimation Equations; NRS = Numeric rating scale.

Reference Listing: 16.2.6.1

Programming notes:

- Include all observed data for Week 4, 8, 12, and 18.
- Rows for column dosing (column dosing will only be added if Stage 4 is initiated.

Final 1.0 | 12-Jul-2023 | Page 48 of 205

^[1] Lower limit of 1-sided 90% CL and upper limit of 1-sided 80% CL.

^[2] P-value is derived from the following model: GEE using Time, Treatment, Treatment*Time and Co-medication type as covariates, with dependent binary variable indicating whether weekly average pain NRS has >=30% decrease from Baseline.

[figure not shown]

Table 14.2.7.1 Daily Pain NRS Responder Analysis (≥50%): Cochran-Mantel Haenszel (Observed Cases) mITT Population

Cochran-Mantel-Haenszel Test

Visit/	Number of		95% CI of Risk	2-sided
Category	Subjects (%)	Risk Difference [1]	Difference	P-value [2]
Week 4			•	
>=50% decrease from Baseline	xx (xx.x%)	X.XX	[x.xx to x.xx]	0.xxxx
Week 8				
>=50% decrease from Baseline	xx (xx.x%)	X.XX	[x.xx to x.xx]	0.xxxx
Week 12				
>=50% decrease from Baseline	xx (xx.x%)	X.XX	[x.xx to x.xx]	0.xxxx
	,			
Week 18	(0/)			0
>=50% decrease from Baseline	xx (xx.x%)	X.XX	[x.xx to x.xx]	0.xxxx

CI = confidence interval; NRS = numeric rating scale.

Programming notes:

• Include all observed data for Week 4, 8, 12, and 18.

^[1] Common effect for the strata (co-medication type*median Baseline Pain NRS) specific risk difference, representing common difference in probability across strata.

^[2] P-value < 0.05 indicates a significant association between number of subjects with >=50% decrease from Baseline and treatment across strata. Reference Listing: 16.2.6.1

[figure not shown]

Table 14.2.7.2 Daily Pain NRS Responder Analysis (≥50%): GEE Analysis (Observed Cases) mITT Population

Programming notes:

- Same shell as Table 14.2.6.3. Change footnote in [2] as: "p-value is derived from the following model: GEE using Time, Treatment, Treatment*Time and Co-medication type as covariates, with dependent binary variable indicating whether weekly average pain NRS has >=50% decrease from Baseline".
- Include all observed data for Week 4, 8, 12, and 18.
- Rows for column dosing (column dosing will only be added if Stage 4 is initiated.

Final 1.0 | 12-Jul-2023 | Page 50 of 205

[figure not shown]

Table 14.2.8.1
Patient Global Impression of Change: Summary Statistics
mITT Population

	Placebo		MEDI7352		Total
Visit/		CCI	CCI	CCI	
Statistic	(N=xx)	(N=xx)	(N=xx)	(N=xx)	(N=XX)
Week 4					
Number of PGIC Responders	xx(xx.x%)	xx(xx.x%)	xx(xx.x%)	xx(xx.x%)	xx (xx.x%)
Very Much Improved	xx(xx.x%)	xx(xx.x%)	xx (xx.x%)	xx (xx.x%)	xx (xx.x%)
Much Improved	xx(xx.x%)	xx(xx.x%)	xx (xx.x%)	xx (xx.x%)	xx (xx.x%)
Minimally Improved	xx(xx.x%)	xx (xx.x%)	xx (xx.x%)	xx (xx.x%)	xx (xx.x%)
No change	xx(xx.x%)	xx (xx.x%)	xx (xx.x%)	xx (xx.x%)	xx (xx.x%)
Minimally Worse	xx(xx.x%)	xx(xx.x%)	xx (xx.x%)	xx (xx.x%)	xx(xx.x%)
Much Worse	xx (xx.x%)				
Very Much Worse	xx(xx.x%)	xx (xx.x%)	xx (xx.x%)	xx (xx.x%)	xx (xx.x%)

Week 8

. . .

N = number of subjects per treatment group; PGIC = Patient Global Impression of Change.

Note: Percentages for Number of subjects in the different improvement categories relative to baseline are n/Number of Subjects by treatment group at each visit *100.

Reference Listing: 16.2.6.6

Programming notes:

- Include all observed data on PGIC scores for Week 4, 8, 12 and 18.
- A column for CCI dosing (CCI) will only be added if Stage 4 is initiated.

Final 1.0 | 12-Jul-2023 | Page 51 of 205

[figure not shown]

[figure not shown]

Table 14.2.8.2 Patient Global Impression of Change: Cochran-Mantel Haenszel mITT Population

Cochran-Mantel-Haenszel Test

Visit/	Number of		95% CI of Risk	2-sided
Category	Patients (%)	Risk Difference [1]	Difference	P-value [2]
Week 4				
Improved relative to Baseline	xx (xx.x%)	X.XX	[x.xx to x.xx]	0.xxxx
Much Improved relative to Baseline	xx (xx.x%)	X.XX	[x.xx to x.xx]	0.xxxx
Very Much improved relative to Baseline	xx (xx.x%)	X.XX	[x.xx to x.xx]	0.xxxx
Week 8				
Improved relative to Baseline	xx (xx.x%)	X.XX	[x.xx to x.xx]	0.xxxx
Much Improved relative to Baseline	xx (xx.x%)	X.XX	[x.xx to x.xx]	0.xxxx
Very Much improved relative to Baseline	xx (xx.x%)	X.XX	[x.xx to x.xx]	0.xxxx
Week 12				
Improved relative to Baseline	xx (xx.x%)	X.XX	[x.xx to x.xx]	0.xxxx
Much Improved relative to Baseline	xx (xx.x%)	X.XX	[x.xx to x.xx]	0.xxxx
Very Much improved relative to Baseline	xx (xx.x%)	X.XX	[x.xx to x.xx]	0.xxxx

Final 1.0 | 12-Jul-2023 | Page 52 of 205

Week 18

Improved relative to Baseline	xx (xx.x%)	X.XX	[x.xx to x.xx]	0.xxxx
Much Improved relative to Baseline	xx (xx.x%)	x.xx	[x.xx to x.xx]	0.xxxx
Very Much improved relative to Baseline	xx (xx.x%)	X.XX	[x.xx to x.xx]	0.xxxx

CI = confidence interval; NRS = numeric rating scale.

[figure not shown]
Programming Notes:

• Include all observed data on PGIC scores for Week 4, 8, 12 and 18.

Final 1.0 | 12-Jul-2023 | Page 53 of 205

^[1] Common effect for the strata (co-medication type*median Baseline Pain NRS) specific risk difference, representing common difference in probability across strata.

^[2] P-value < 0.05 indicates a significant association between improvement relative to Baseline and treatment across strata. Reference Listing: 16.2.6.6

[figure not shown]

5. Exploratory Efficacy Analyses

[figure not shown]
Final 1.0 | 12-Jul-2023 | Page 54 of 205

Final 1.0 | 12-Jul-2023 | Page 55 of 205

[figure not shown]
6. Safety and Tolerability

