2.2.4. Other Endpoints

The following endpoints will be assessed:

- Change in the weekly average of the average daily pain scores from the baseline week to Week 12, as measured on an 11-point (0-10) NRS, versus dose.
- Immunogenicity (ADA) assessments.

3. Overall Study Design and Plan

This is a randomised, double-blind, placebo-controlled study of MEDI7352 in subjects with moderate to severe chronic PDN persistent for 6 months or longer, not adequately controlled by standard of care treatments, caused by type 1 or type 2 diabetes mellitus. The study incorporates a screening period of up to 45 days and a 12-week double-blind treatment period during which MEDI7352 or placebo will be administered intravenously (IV) on 6 occasions, with each dose separated by 14 days. There will be a 6-week follow-up period.

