8.2. Secondary Efficacy Analysis

The MMRM model outlined in Section 8.1 will be applied for secondary endpoints using observed cases:

[figure not shown]
- Change in Galer NPS total score from baseline to Days 28, 56, and 84 of treatment and the follow-up visit.
- Change in DSIS from baseline to Days 28, 56, and 84 of treatment and the follow-up visit.
- Change in the eight SF-36 parameters from baseline to Day 84 of treatment.

A GEE approach for binary data will be used for the following dichotomous endpoints:

- Percentage of subjects who have achieved ≥30% reductions in the weekly average of the average daily pain score from baseline during Weeks 4, 8, and 12 of treatment and the week before follow-up.
- Percentage of subjects who have achieved ≥50% reductions in the weekly average of the average daily pain score from baseline during Weeks 4, 8, and 12 of treatment and the week before follow-up.

The GEE model specification will include a binomial distribution, a logit link function, and an unstructured covariance matrix. If this analysis fails to converge, a simpler structure (e.g. first-order autoregressive or compound symmetry structures) will be found using AIC. The model will include terms for:

- co-medication type (as a factor)
- treatment (as a factor)
- time (as a factor)
- the interaction between treatment and time

A CMH test stratified by the crossing of co-medication subgroup and median baseline pain score will also be carried out for the above dichotomous endpoints. The CMH risk difference at Week 12 will be estimated between the treatment group and placebo. The number and percentage of subjects meeting the reduction response will be displayed, along with the risk difference, 95% CI and *P* value.

[figure not shown]
The proportion of subjects who have 'improved', 'much improved,' or 'very much improved' relative to baseline on the PGIC on Days 28, 56, and 84 of treatment and the follow-up visit will be tested using a CMH statistics.

The efficacy analysis of secondary endpoints will be based on the observed cases and on the mITT population.

Usage of rescue medication (yes/no) will be summarized by dose group for each visit from baseline to Week 12 of treatment and over the whole treatment period. The following additional variables will be derived and summarised:

- Total number of days rescue medication was used.
 - Each day on which rescue medication was used at least once is counted.

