CI = Confidence interval; LS = least square; NRS = Numeric rating scale.

Programming Notes:

- Include LSmeans and difference in Lsmean with Placebo in repeated tables for the Treatment*Week interaction.
- Rows for column dosing (column dosing will only be added if Stage 4 is initiated.

Final 1.0 | 12-Jul-2023 | Page 31 of 205

^[3] The LS mean is a model estimate using fitted group parameter and the baseline weekly average pain NRS parameter evaluated at the grand mean over each group. Reference Listing: 16.2.6.1

[figure not shown]

[figure not shown]

Table 14.2.1.3.2 Daily Pain NRS: Sensitivity of Primary MCP-Mod Analysis (BOCF) mITT Population

Programming Notes:

- Same shell as Table 14.2.1.2.1, substituting "LOCF = Last Observation Carried Forward" by "BOCF = Baseline Observation Carried Forward".
- The MCP-MOD approach will only be performed if stage 4 is initiated, otherwise there would be insufficient dosing data to fit the non-linear models.

Final 1.0 | 12-Jul-2023 | Page 32 of 205

[figure not shown]
4. Secondary Efficacy Analysis

Table 14.2.2.1
Galer NPS: Summary Statistics (Observed Cases)
mITT Population

Parameter: xxxxx					
	Placebo		MEDI7352		Total
Visit/		CCI	CCI	CCI	
Statistic	(N=xx)	(N=xx)	(N=xx)	(N=xx)	(N=xx)
Baseline [1]					
n	XX	XX	XX	XX	XX
Mean (SD)	xx.x (xx.xx)	xx.x (xx.xx)	xx.x(xx.xx)	xx.x (xx.xx)	xx.x (xx.xx)
Median	XX.X	XX.X	XX.X	XX.X	XX.X
Q1, Q3	XX.X, XX.X	XX.X, XX.X	XX.X, XX.X	XX.X, XX.X	XX.X, XX.X
Min, Max	xx, xx	xx, xx	xx, xx	xx, xx	XX, XX
Week 4					
n	XX	XX	XX	XX	XX
Mean (SD)	xx.x(xx.xx)	xx.x(xx.xx)	xx.x(xx.xx)	xx.x(xx.xx)	xx.x (xx.xx)
Median	XX.X	XX.X	XX.X	XX.X	XX.X
Q1, Q3	XX.X, XX.X	XX.X, XX.X	XX.X, XX.X	XX.X, XX.X	XX.X, XX.X
Min, Max	xx, xx	xx, xx	xx, xx	xx, xx	XX, XX
Week 4 CFB					
n	XX	XX	XX	XX	XX
Mean (SD)	xx.x (xx.xx)	xx.x (xx.xx)	xx.x(xx.xx)	xx.x (xx.xx)	xx.x (xx.xx)
Median	XX.X	XX.X	XX.X	xx.x	XX.X
Q1, Q3	xx.x, xx.x	xx.x, xx.x	XX.X, XX.X	xx.x, xx.x	XX.X, XX.X
Min, Max	XX, XX	xx, xx	xx, xx	xx, xx	xx, xx

•••

Final 1.0 | 12-Jul-2023 | Page 33 of 205

feel a single type of pain only sometimes

xx(xx.x%)

xx (xx.x%) xx (xx.x%)

xx(xx.x%)

For Pain Duration Frequency

Baseline [1]				
I feel a background pain all of the time and occasional flare-ups	xx (xx.x%)	xx (xx.x%)	xx (xx.x%)	xx (xx.x%)
I feel a single type of pain all the time	xx (xx.x%)	xx(xx.x%)	xx(xx.x%)	xx(xx.x%)

Week 4

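### The v1.0 responder shells do not assure a result for each dose versus placebo at Week 12: the GEE dose rows carry no week, and the CMH rows carry no dose

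*SAP*

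**What the plan says.** SAP Section 8.2 (v1.1, with the same wording in v1.0) defines the responder endpoints as ≥30% and ≥50% reductions in weekly average pain "from baseline during Weeks 4, 8, and 12 of treatment and the week before follow-up". They are analysed by GEE with terms for co-medication, treatment, time and "the interaction between treatment and time". A stratified CMH test is added: "The CMH risk difference at Week 12 will be estimated between the treatment group and placebo".

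The v1.0 shell for GEE Table 14.2.6.2 names the same model: "P-value is derived from the following model: GEE using Time, Treatment, Treatment*Time and Co-medication type as covariates". Its programming note is "Include all observed data for Week 4, 8, 12, and 18". Week, Treatment and Treatment*Week have only degrees of freedom and a joint p-value. Below them is one row per dose, for example "Active 450 mcg vs Placebo", with estimate, standard error, interval and p-value. No row names a week. Table 14.2.7.2 (≥50%) reuses this layout, although it cites the shell as 14.2.6.3, which is not in the table list.

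The v1.0 shell for CMH Table 14.2.7.1 has one line for each of Weeks 4, 8, 12 and 18. Each line holds a single count, risk difference, interval and p-value. There is no dose or placebo row or column. Table 14.2.6.1 has the same layout as far as it is legible.

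The MMRM shells for pain, NPS, DSIS and SF-36 are built differently. They have the same unlabelled dose rows, plus a by-week block. The note for pain reads "Include LSmeans and difference in Lsmean with Placebo in repeated tables for the Treatment*Week interaction".

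**The concern.** These are named secondary endpoints in a dose-response study, and each is tied to specific weeks. A reader will expect a responder comparison for each dose against placebo at Week 12. The GEE table has doses but no week, and the CMH table has weeks but no dose, so neither layout fixes that result.

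Nothing else fills the gap. These four are the only responder tables in the efficacy list, and none shows responder percentages by arm. PGIC, by contrast, has a separate per-arm summary (Table 14.2.8.1).

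What is at stake is the meaning of the reported odds ratio and p-value, which would be settled by a coding default at programming. A Week 12 effect of one dose could be diluted or not shown at all.

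**Working it through.** **Timing.** The last dose is on Day 70, which is Week 10 (70/7 = 10). Treatment lasts 12 weeks and then "There will be a 6-week follow-up period" (Section 3), so follow-up ends at Week 18 (12 + 6). Week 18 is 8 weeks after the last dose (18 − 10).

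**What the single GEE row estimates.** With treatment, week and their interaction in a logit model, the log odds ratio for a dose at week w is β(dose) + γ(dose, w).
- Under reference-level coding γ is zero at the reference week, so the dose row is the effect at that week only.
- Under an averaging (LS-means) contrast, the row is the mean of the weekly log odds ratios.

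The shell specifies neither. The joint interaction p-value does not allow a weekly contrast to be recovered.

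**Illustration 1.** The SAP gives no responder rates, so these are assumptions: 50% active and 30% placebo at Weeks 4, 8 and 12, equal rates at Week 18, and no co-medication effect.
- Week 12: odds ratio (0.5/0.5)/(0.3/0.7) = 2.33, log 0.847.
- Average of four weeks: (3 × 0.847 + 0)/4 = 0.635, odds ratio 1.89.
- Week 18 as reference: log 0, odds ratio 1.00.

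**Illustration 2.** Assumed rates at Weeks 4/8/12/18 are 25/30/30/30% on placebo and 35/42/50/30% on active. A logistic model with treatment by week was fitted to independent simulated data, 20,000 per arm and week. Only the coding was changed.

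| Coding | Treatment coefficient (log odds ratio) |
|---|---|
| Reference Week 4 | 0.476 |
| Reference Week 12 | 0.842 |
| Reference Week 18 | −0.008 |
| Average over four weeks | 0.462 |

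**Range.** The rates are as in Illustration 2, but with active response at Week 18 set to 30%, 40% or 50%. The four-week average odds ratio is then 1.59, 1.77 or 1.96, against 2.33 at Week 12 each time. The average falls short even when the Week 12 effect persists fully, because Weeks 4 and 8 also enter it.

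**CMH text and shell side by side.** Section 8.2 promises a Week 12 risk difference against placebo, with the number and percentage of responders. The shell has one cell for each of these per visit. A risk difference needs two groups, and the GEE shell's 3 degrees of freedom for Treatment imply three active doses plus placebo. One cell cannot hold three dose comparisons, and neither text nor shell says which comparison it holds.

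**The case against.** The model itself is sound. Treatment by week contains every weekly dose contrast. Week 18 belongs in it because follow-up is part of the endpoint, and with the interaction its inclusion does not bias a Week 12 contrast. The fault is in the output layout, and the SAP allows programming notes to be added to shells. The endpoints are secondary and have no multiplicity control. The main efficacy analysis is MCP-Mod on Week 12 change in pain, with per-dose estimates from the ANCOVA. All of this stands, and it limits the consequence.

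Three stronger readings are tempting, and the documents do not support them.
- A reader might infer that the GEE row is not the Week 12 effect. It would be if Week 12 were made the reference level. What can be said is that the week is unspecified.
- A reader might infer that the CMH pools the doses and so dilutes an active one heavily. Pooling is stated nowhere. Section 6.1.2 speaks of dose group, Section 8.1.1 plans pairwise comparisons with placebo, and the singular in Section 8.2 may simply mean each treatment group in turn. A halving of the risk difference by an equally large inactive lowest dose would not fit the design either. Stage 1, which studies the lowest dose, has about 10 subjects including placebo, against 37, 51 and 67 evaluable in the later dose arms.
- A reader might infer that the current shells carry the same layout. The v1.1 shells at hand stop before the efficacy tables, so this cannot be checked.

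**Conclusion.** The point holds for the v1.0 shells and for Section 8.2 in both SAP versions. Followed as written, the GEE tables give one effect per dose at an unspecified week or over a mixture of on- and off-treatment weeks. The CMH tables give a Week 12 figure not tied to any dose. A Week 12 responder result for each dose versus placebo is therefore not assured.

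Under the first set of assumed rates, one true pattern could be reported as an odds ratio of 2.33, 1.89 or 1.00 according to coding alone. These figures show sensitivity and are not forecasts: they rest on invented responder rates and, for 1.00, on complete loss of effect by Week 18 together with Week 18 as reference. No sample size, power or type I error figure in the SAP is affected. The layout should be corrected before the tables are programmed, but the primary analysis does not depend on it.

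**What to change.** - **Tables 14.2.6.2 and 14.2.7.2:** replace the single dose rows with odds ratio, 95% CI and p-value for each dose versus placebo at Weeks 4, 8 and 12. Show Week 18 separately, labelled as follow-up. A programming note like the one in the MMRM shells would do this. Correct the cross-reference to 14.2.6.3.
- **Tables 14.2.6.1 and 14.2.7.1:** give responder counts and percentages per arm, and a risk difference with 95% CI and p-value for each dose versus placebo at each visit.
- **Section 8.2:** state that the CMH risk difference is estimated between each dose group and placebo.
- **Shells v1.1:** check that they carry the same changes.

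The cost is shell and SAP wording, extra estimate statements from the same fitted GEE, and pairwise CMH runs on the same data. No new data are needed.

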6.1. Displays of Adverse Events

Table 14.3.1.1 Summary of Overall Adverse Events Safety Population

	Placebo		ME	DI7352		Total
Character	(NI)	CCI	CCI (N)	CCI	All MEDI7352	(NI)
Category	(N=xx)	(N=xx)	(N=xx)	(N=xx)	(N=xx)	(N=xx)
Subjects with any AE	xx (xx.x%)	xx (xx.x%)				
Subjects with any TEAE	xx (xx.x%)	xx (xx.x%)				
TEAE categorized as Mild	xx (xx.x%)	xx (xx.x%)				
TEAE categorized as Moderate	xx (xx.x%)	xx (xx.x%)	xx(xx.x%)	xx(xx.x%)	xx (xx.x%)	xx (xx.x%)
TEAE categorized as Severe	xx (xx.x%)	xx (xx.x%)				
Subjects with any SAE	xx (xx.x%)	xx (xx.x%)				
Subjects with any SAE possibly related to IP [1]	xx (xx.x%)	xx (xx.x%)				
Subjects with any TEAE leading to Discontinuation of IP	xx (xx.x%)	xx (xx.x%)				
Subjects with any TEAE related to IP	xx (xx.x%)	xx (xx.x%)				
TEAE categorized as Mild related to IP	xx (xx.x%)	xx (xx.x%)				
TEAE categorized as Moderate related to IP	xx (xx.x%)	xx (xx.x%)				
TEAE categorized as Severe related to IP	xx (xx.x%)	xx (xx.x%)				
Subjects with any SAE leading to Death	xx (xx.x%)	xx (xx.x%)				

Final 1.0 | 12-Jul-2023 | Page 56 of 205

AE = adverse event; IP = Investigational product, N = number of subjects per treatment group; SAE = serious adverse event; TEAE = treatment emergent adverse event.

[1] Possibly related is defined as with reasonable possibility that the AE was caused by the IP, as assessed by investigator Note: Subjects who reported more than one adverse event within each category were only counted once. A TEAE is defined as an adverse event with an onset at the time of or following the start of treatment with IP.

Reference Listing: 16.2.7.1, 16.2.7.2, 16.2.7.3, 16.2.7.4

Programming Notes:

• A column for doing (column f

Final 1.0 | 12-Jul-2023 | Page 57 of 205

[figure not shown]

Table 14.3.1.2
Treatment Emergent Adverse Events by System Organ Class and Preferred Term Safety Population

System Organ Class	Placebo		M	IEDI7352		Total
		CCI	CCI	CCI	All MEDI7352	
Preferred Term	(N=xx)	(N=xx)	(N=xx)	(N=xx)	(N=xx)	(N=xx)
Subjects with at Least One TEAE	xx (xx.x%) xx	xx (xx.x%) xx	xx (xx.x%) xx	xx (xx.x%) xx	xx (xx.x%) xx	xx (xx.x%) xx
System Organ Class 1	xx (xx.x%) xx	xx (xx.x%) xx	xx (xx.x%) xx	xx (xx.x%) xx	xx (xx.x%) xx	xx (xx.x%) xx
Preferred Term 1	xx (xx.x%) xx	xx (xx.x%) xx	xx (xx.x%) xx	xx (xx.x%) xx	xx (xx.x%) xx	xx (xx.x%) xx
Preferred Term 2	xx (xx.x%) xx	xx (xx.x%) xx	xx (xx.x%) xx	xx (xx.x%) xx	xx (xx.x%) xx	xx (xx.x%) xx
Preferred Term 3	xx (xx.x%) xx	xx (xx.x%) xx	xx (xx.x%) xx	xx (xx.x%) xx	xx (xx.x%) xx	xx (xx.x%) xx
System Organ Class 2	xx (xx.x%) xx	xx (xx.x%) xx	xx (xx.x%) xx	xx (xx.x%) xx	xx (xx.x%) xx	xx (xx.x%) xx
Preferred Term 1	xx (xx.x%) xx	xx (xx.x%) xx	xx (xx.x%) xx	xx (xx.x%) xx	xx (xx.x%) xx	xx (xx.x%) xx
Preferred Term 2	xx (xx.x%) xx	xx (xx.x%) xx	xx (xx.x%) xx	xx(xx.x%)xx	xx (xx.x%) xx	xx (xx.x%) xx
Preferred Term 3	xx (xx.x%) xx	xx (xx.x%) xx	xx (xx.x%) xx	xx (xx.x%) xx	xx (xx.x%) xx	xx (xx.x%) xx
System Organ Class 3 Preferred Term 1	xx (xx.x%) xx xx (xx.x%) xx	XX (XX.X%) XX	xx (xx.x%) xx	$XX (XX.X^{0}\%) XX$	XX (XX.X%) XX	XX (XX.X%) XX
Preferred Term 2	` /	xx (xx.x%) xx	xx (xx.x%) xx	xx (xx.x%) xx	xx (xx.x%) xx	xx (xx.x%) xx
Preferred Term 2 Preferred Term 3	xx (xx.x%) xx xx (xx.x%) xx	xx (xx.x%) xx xx (xx.x%) xx	xx (xx.x%) xx xx (xx.x%) xx	xx (xx.x%) xx $xx (xx.x%) xx$	xx (xx.x%) xx $xx (xx.x%) xx$	xx (xx.x%) xx xx (xx.x%) xx

AE = adverse event; IP = investigational product; MedDRA = Medical Dictionary for Regulatory Activities; n = number of subjects within each SOC/PT category; N = number of subjects per treatment group; IP = investigational product; PT = Preferred Term; SOC = System Organ Class; TEAE = treatment-emergent adverse event.

Note: Results are n (n/N * 100) then the total number of events.

[figure not shown]
A TEAE is defined as AE with an onset at the time of or following the start of treatment with IP.

Aes were coded using MedDRA version 26.0. Subjects are counted once for each SOC and once for each PT.

Aes are displayed by descending frequency of SOC, then descending frequency of PT within SOC, based on 'All MEDI7352' column. Table is sorted by international order for SOC of same frequency, and alphabetically for PT of same frequency.

Reference Listing: 16.2.7.1

Final 1.0 | 12-Jul-2023 | Page 58 of 205

- SOC and PT texts should be in proper case in table.
- In case a term is not coded (e.g. in a dry run) it will be labelled as "Not Coded [SOC]" and "Not Coded [PT]", and sorted at the end of the table.
- A column for column for column dosing (column for column for col

Final 1.0 | 12-Jul-2023 | Page 59 of 205

[figure not shown]

Table 14.3.1.3

Treatment Emergent Adverse Events by Severity, System Organ Class and Preferred Term
Safety Population

System Organ Class Preferred Term	Placebo MEDI7352						
Severity		CCI	CCI CCI All MEDI7352				
	(N=xx)	(N=xx)	(N=xx)	(N=xx)	(N=xx)	(N=xx)	
Subjects with at Least One TEAE	xx (xx.x%)	xx (xx.x%)	xx (xx.x%)	xx (xx.x%)	xx (xx.x%)	xx (xx.x%)	
Mild	xx (xx.x%)	xx (xx.x%)	xx (xx.x%)	xx (xx.x%)	xx(xx.x%)	xx (xx.x%)	
Moderate	xx (xx.x%)	xx (xx.x%)	xx (xx.x%)	xx (xx.x%)	xx(xx.x%)	xx (xx.x%)	
Severe	xx (xx.x%)	xx (xx.x%)	xx (xx.x%)	xx (xx.x%)	xx (xx.x%)	xx (xx.x%)	
System Organ Class 1	xx (xx.x%)	xx (xx.x%)	xx (xx.x%)	xx (xx.x%)	xx (xx.x%)	xx (xx.x%)	
Mild	xx (xx.x%)	xx (xx.x%)	xx (xx.x%)	xx (xx.x%)	xx(xx.x%)	xx (xx.x%)	
Moderate	xx (xx.x%)	xx (xx.x%)	xx (xx.x%)	xx (xx.x%)	xx(xx.x%)	xx (xx.x%)	
Severe	xx (xx.x%)	xx (xx.x%)	xx (xx.x%)	xx (xx.x%)	xx (xx.x%)	xx (xx.x%)	
Preferred Term 1	xx (xx.x%)	xx (xx.x%)	xx (xx.x%)	xx (xx.x%)	xx (xx.x%)	xx (xx.x%)	
Mild	xx (xx.x%)	xx (xx.x%)	xx (xx.x%)	xx (xx.x%)	xx(xx.x%)	xx (xx.x%)	
Moderate	xx (xx.x%)	xx (xx.x%)	xx (xx.x%)	xx (xx.x%)	xx(xx.x%)	xx (xx.x%)	
Severe	xx (xx.x%)	xx (xx.x%)	xx(xx.x%)	xx (xx.x%)	xx(xx.x%)	xx (xx.x%)	

AE = adverse event; IP = investigational product; MedDRA = Medical Dictionary for Regulatory Activities; ; n = number of subjects within each SOC/PT/Severity category; N = number of subjects per treatment group; PT = Preferred Term; SOC = System Organ Class; TEAE = treatment-emergent adverse event.

Note: Results are n (n/N * 100).

[figure not shown]
A TEAE is defined as an AE with an onset at the time of or following the start of treatment with IP.

Aes were coded using MedDRA version 26.0. Subjects are counted once for each SOC and once for each PT at the maximum severity.

Aes are displayed by descending frequency of SOC, then descending frequency of PT within SOC, based on 'All MEDI7352' column. Table is sorted by international order for SOC of same frequency, and alphabetically for PT of same frequency.

Reference Listing 16.2.7.1

Final 1.0 | 12-Jul-2023 | Page 60 of 205

- SOC and PT texts should be in proper case in table.
- Present only severity categories with at least one subject.
- In case a term is not coded (e.g. in a dry run) it will be labelled as "Not Coded [SOC]" and "Not Coded [PT]", and sorted at the end of the table. SOC.
- A column for CCI dosing (CCI) will only be added if Stage 4 is initiated.

Final 1.0 | 12-Jul-2023 | Page 61 of 205

[figure not shown]

Table 14.3.1.4

Treatment Emergent Adverse Events by Relationship to Study Medication, System Organ Class and Preferred Term Safety Population

			outery I opulation				
System Organ Class Preferred Term	Placebo MEDI7352						
Relatedness	(N=xx)	(N=xx)			All MEDI7352 (N=xx)	(N=xx)	
Subjects with at Least One TEAE	xx (xx.x%)	xx (xx.x%)	xx (xx.x%)	xx (xx.x%)	xx (xx.x%)	xx (xx.x%)	
Not Related	xx (xx.x%)	xx (xx.x%)	xx(xx.x%)	xx (xx.x%)	xx(xx.x%)	xx (xx.x%)	
Related [1]	xx (xx.x%)	xx (xx.x%)	xx (xx.x%)	xx (xx.x%)	xx (xx.x%)	xx (xx.x%)	
System Organ Class 1	xx (xx.x%)	xx (xx.x%)	xx (xx.x%)	xx (xx.x%)	xx (xx.x%)	xx (xx.x%)	
Not Related	xx (xx.x%)	xx (xx.x%)	xx (xx.x%)	xx (xx.x%)	xx(xx.x%)	xx (xx.x%)	
Related [1]	xx (xx.x%)	xx (xx.x%)	xx (xx.x%)	xx (xx.x%)	xx (xx.x%)	xx (xx.x%)	
Preferred Term 1	xx (xx.x%)	xx (xx.x%)	xx (xx.x%)	xx (xx.x%)	xx (xx.x%)	xx (xx.x%)	
Not Related	xx (xx.x%)	xx (xx.x%)	xx (xx.x%)	xx (xx.x%)	xx(xx.x%)	xx (xx.x%)	
Related [1]	xx (xx.x%)	xx (xx.x%)	xx(xx.x%)	xx (xx.x%)	xx(xx.x%)	xx (xx.x%)	

. . .

AE = adverse event; IP = investigational product; MedDRA = Medical Dictionary for Regulatory Activities; n = number of subjects within each SOC/PT/Relatedness category; N = number of subjects per treatment group; PT = Preferred Term; SOC = System Organ Class; TEAE = treatment-emergent adverse event.

[1] Related is defined as reasonable possibility that the AE was caused by investigational product, as assessed by the investigator. Note: Results are n (n/N *100).

[figure not shown]
A TEAE is defined as an AE with an onset at the time of or following the start of treatment with IP.

Aes were coded using MedDRA version 26.0. Subjects are counted once for each SOC and once for each PT for the most related AE.

Aes are displayed by descending frequency of SOC, then descending frequency of PT within SOC, based on 'All MEDI7352' column. Table is sorted by international order for SOC of same frequency, and alphabetically for PT of same frequency.

Reference Listing 16.2.7.1

Final 1.0 | 12-Jul-2023 | Page 62 of 205

- SOC and PT texts should be in proper case in table.
- Present only severity categories with at least one subject.
- In case a term is not coded (e.g. in a dry run) it will be labelled as "Not Coded [SOC]" and "Not Coded [PT]", and sorted at the end of the table. SOC.
- A column for column dosing (column dosing will only be added if Stage 4 is initiated.

Final 1.0 | 12-Jul-2023 | Page 63 of 205

[figure not shown]

Table 14.3.1.5

Treatment Emergent Adverse Events by ADA Status Category, System Organ Class and Preferred Term Safety Population

Treatment: xxxxxxx

	ADA		TE-ADA	Non-TE-	TE Persistently	TE Transiently	Post-Baseline and Baseline	Only Baseline
System Organ Class	Negative	ADA Positive	Positive	ADA Positive	ADA Positive	ADA Positive	Positive	Positive
Preferred Term	(N=xx)	(N=xx)		(N=xx)			(N=xx)	(N=xx)
Freiened Tenn	(IN-XX)	(IN-XX)	(N=xx)	(IN-XX)	(N=xx)	(N=xx)	(IN-XX)	(IN-XX)
Subjects with at Least One TEAE	xx (xx.x%) xx	xx (xx.x%) xx	xx (xx.x%) xx	xx (xx.x%) xx				
System Organ Class 1	xx (xx.x%) xx	xx (xx.x%) xx	xx (xx.x%) xx	xx (xx.x%) xx				
Preferred Term 1	xx (xx.x%) xx	,	` /	xx (xx.x%) xx	` /	` /	` /	` /
Preferred Term 2	` /	xx (xx.x%) xx		, ,				
Preferred Term 3	` /	xx (xx.x%) xx	` /	` /	` /	` /	` /	` /
System Organ Class 2	xx (xx.x%) xx	xx (xx.x%) xx	xx (xx.x%) xx	xx (xx.x%) xx				
Preferred Term 1	` /	xx (xx.x%) xx	` /	` /	` /	` /	` /	` /
Preferred Term 2	` /	xx (xx.x%) xx	` /	` /	` /	` /	` /	` /
Preferred Term 3		xx (xx.x%) xx						
System Organ Class 3	xx (xx.x%) xx	xx (xx.x%) xx	xx (xx.x%) xx	xx (xx.x%) xx				
Preferred Term 1	xx (xx.x%) xx			xx (xx.x%) xx				, ,
Preferred Term 2	xx (xx.x%) xx	xx (xx.x%) xx	` /		` /	` /	` /	` /
Preferred Term 3	` /	xx (xx.x%) xx	` /	` /	` /	` /	` /	` /

AE = adverse event; ADA = Anti-Drug Antibodies; IP = investigational product; MedDRA = Medical Dictionary for Regulatory Activities; ; n = number of subjects within each SOC/PT category; N = number of subjects per ADA status category; PT = Preferred Term; SOC = System Organ Class; TEAE = treatment-emergent adverse event.

ADA categories are defined in the Statistical Analysis Plan.

[figure not shown]
Note: Results are n (n/N *100) then the total number of events.

A TEAE is defined as an AE with an onset at the time of or following the start of treatment with IP.

Aes were coded using MedDRA version 26.0. Subjects are counted once for each SOC and once for each PT.

Table is sorted by international order for SOC, and alphabetically for PT.

Reference Listing: 16.2.7.1

- SOC and PT texts should be in proper case in table.
- Repeat for Placebo, occurrence and Overall.
- In case a term is not coded (e.g. in a dry run) it will be labelled as "Not Coded [SOC]" and "Not Coded [PT]", and sorted at the end of the table. SOC.
- A table for column dosing (column dosing (column dosing dosing

Table 14.3.1.6

Treatment Emergent Adverse Events Leading to Discontinuation of Study Drug by System Organ Class and Preferred Term Safety Population

Programming Notes:

- Same shell as Table 14.3.1.2. Change first row to be "Subjects with at Least One TEAE leading to IP discontinuation".
- Update Reference Listing to 16.2.7.2.
- A column for column dosing (Column dosing will only be added if Stage 4 is initiated.

Table 14.3.1.7

Non-Serious Adverse Events Occurring in More than 5% of Subjects by System Organ Class and Preferred Term Safety Population

Programming Notes:

- Same shell as Table 14.3.1.2. Change first row to be "Subjects with at Least One Non-Serious AE" and remove references to TEAEs.
- Update Reference Listing to 16.2.7.1.
- A column for column for dosing (column for dosing

Final 1.0 | 12-Jul-2023 | Page 65 of 205

[figure not shown]

Table 14.3.1.8

Treatment Emergent Adverse Events Occurring in More than 5% of Subjects by Preferred Term Safety Population

			Safety I opulation	I .			
	Placebo	Placebo MEDI7352					
Preferred Term	(N=xx)	(N=xx)	(N=xx)	(N=xx)	All MEDI7352 (N=xx)	(N=xx)	
Subjects with at Least One TEAE	xx (xx.x%) xx	xx (xx.x%) xx	xx (xx.x%) xx	xx (xx.x%) xx	xx (xx.x%) xx	xx (xx.x%) xx	
Preferred Term 1	xx (xx.x%) xx	xx (xx.x%) xx	xx (xx.x%) xx	xx (xx.x%) xx	xx (xx.x%) xx	xx (xx.x%) xx	
Preferred Term 2	xx (xx.x%) xx	xx (xx.x%) xx	xx (xx.x%) xx	xx (xx.x%) xx	xx (xx.x%) xx	xx (xx.x%) xx	
Preferred Term 3	xx (xx.x%) xx	xx (xx.x%) xx	xx (xx.x%) xx	xx (xx.x%) xx	xx (xx.x%) xx	xx (xx.x%) xx	
•••							

 $AE = adverse \ event; IP = investigational \ product; MedDRA = Medical \ Dictionary \ for \ Regulatory \ Activities; n = number \ of \ subjects \ within \ each \ PT \ category;$

N = number of subjects per treatment group; PT = Preferred Term; TEAE = treatment-emergent adverse event.

Note: Results are n (n/Number of subjects in the Safety population within each PT*100) then the total number of events.

A TEAE is defined as AE with an onset at the time of or following the start of treatment with IP.

Aes were coded using MedDRA version 26.0. Subjects are counted once for each PT.

Aes are displayed by descending frequency of PT based on 'All MEDI7352' column, and alphabetically for PT of same frequency. Reference Listing: 16.2.7.1

Programming Notes:

- PT texts should be in proper case in table.
- In case a term is not coded (e.g., in a dry run) it will be labelled as Not Coded [PT]", and sorted at the end of the table.
- A column for column dosing (column for column for col

[figure not shown]

[figure not shown]

Table 14.3.1.9 Treatment Emergent Adverse Events by Preferred Term Safety Population

Programming Notes:

- Same shell as Table 14.3.1.8.
- Display all TEAEs, not only the most common.
- PT texts should be in proper case in table.
- In case a term is not coded (e.g., in a dry run) it will be labelled as Not Coded [PT]", and sorted at the end of the table.
- A column for column dosing column dosing will only be added if Stage 4 is initiated.

Final 1.0 | 12-Jul-2023 | Page 67 of 205

